7.0 TREATMENT PLAN

Drug	Dose ^c	Frequency	Route of Administration
Daratumumab	16 mg/kg body weight	Weekly, weeks 1-8	IV infusion
Daratumumab	16 mg/kg body weight	Every 2 weeks, weeks 9-24 ^a	IV infusion
Daratumumab	16 mg/kg body weight	Every 4 weeks, week 25 ^b onwards, for up to 24 months of total study therapy	IV infusion

^a First dose of the every-2-week dosing schedule is given at week 9

^b First dose of the every-4-week dosing schedule is given at week 25

^c Weight from screening visit will be used for initial dosing and throughout treatment period but will be recalculated for weight change $\geq 10\%$.

Infusion rates for daratumumab administration

	Dilution volume	Initial rate (1 st hour)	Rate increment ^a	Maximum rate
First infusion	1000 mL	50 mL/hour	50 mL/hour every hour	200 mL/hour
Second infusion ^b	500 mL	50 mL/hour	50 mL/hour every hour	200 mL/hour
Subsequent infusion ^c	500 mL	100 mL/hour	50 mL/hour every hour	200 mL/hour

^a Consider incremental escalation of the infusion rate only in the absence of infusion reactions.

^b Use a dilution volume of 500 mL only if there were no Grade 1 (mild) or greater infusion reactions during the first 3 hours of the first infusion. Otherwise, continue to use a dilution volume of 1000 mL and instructions for the first infusion.

^c Use a modified initial rate for subsequent infusions (i.e. third infusion onwards) only if there were no Grade 1 (mild) or greater infusion reactions during a final infusion rate of ≥ 100 mL/hr in the first two infusions. Otherwise, continue to use instructions for the second infusion.

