Subjects who are positive for Anti-HBc or Anti-HBs will undergo testing for hepatitis B DNA by PCR. Subjects with serologic findings suggestive of HBV vaccination (Anti-HBs positivity as the only serologic marker) and a known history of prior HBV vaccination do not need to be tested for HBV DNA by PCR. During and following study treatment, subjects who have history of HBV infection will be closely monitored for clinical and laboratory signs of reactivation of HBV as specified in the Time and Events Schedule (Section 9). Where required by local law, the results of HBV testing may be reported to the local health authorities

Management of Hepatitis B Virus Reactivation:

Primary antiviral prophylaxis is permitted as per local standard of care. Per protocol, HBV DNA testing by PCR is mandatory for subjects at risk for HBV reactivation. For subjects who are diagnosed with HBV reactivation while on treatment, study treatment should be interrupted until the infection is adequately controlled. If the benefits outweigh the risks, study treatment may be resumed with concomitant antiviral prophylaxis as per local standard of care. Consult a liver disease specialist as clinically indicated.

7.4 Criteria For Removal From Protocol Treatment:

- 7.4.1 Hematologic progression of disease.
- 7.4.2 Organ progression in the absence of hematologic response
- 7.4.3 Complete hematologic response, with continuation of the study drug per the discretion of the treating investigator
- 7.4.4 Unacceptable toxicity.
- 7.4.5 The patient may withdraw from the study at any time for any reason.
- 7.4.6 Development of overt multiple myeloma.
- 7.4.7 Completion of 24 months of daratumumab.

- 7.5 All patients will be followed until initiation of next treatment.

8.0 **TOXICITIES TO BE MONITORED AND DOSAGE MODIFICATIONS**

See Section 3.0 for potential toxicities associated with daratumumab. In all patients experiencing such toxicities, an attempt should be made to distinguish between drug toxicity, associated medical illness, or disease (amyloid)-related symptomology.

Dose delay is the primary method for managing daratumumab-related toxicities.

Infusion-related reactions:

Infusion reactions of any grade will lead to the temporary interruption or slowing of the infusion, as well as management of symptoms. Depending on the grade/severity of the reaction, this may require the permanent discontinuation of the drug.

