6 Order type and screen and blood bank phenotype on patients prior to starting daratumumab and document in the order that the patient will be receiving daratumumab as notification to Blood Bank due to its interference with serological testing. See Section 7.3.
7 Full history and physical exam with liver measurements required monthly while on protocol. Limited physical examination at other visits only if clinically indicated.

8 If FLCs have normalized, full HAM1-5 panels to be completed at next visit.

9 Screening tests should be performed within 28 days of initiating study drug with the exception of Echocardiogram, CXR, PFTs and EKG, which could occur within 60 days.

10 HBV serology testing: HBsAg, antibody to antiHBs, and antibody to antiHBc assessments should be obtained for those on study treatment for less than 6 months at the time of amendment 11. Subjects who have serologic evidence of HBV exposure, but are HBsAg negative and do not have active HBV infection will have testing monitored every 3 months while on study treatment.

11. HBV DNA testing: Q12W during treatment, at the End of treatment visit, and Q12W for up to 6 months after last dose of study treatment. For subjects with serologic evidence of resolved HBV infection (i.e., positive Anti-HBs or positive Anti-HBc) at Screening, HBV DNA testing by PCR must be performed locally. See section 7.3

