11.0 STATISTICAL CONSIDERATIONS

11.1 Sample Size Estimation

Estimated patient accrual and trial duration: The study will be designed as a single armed phase II trial, in which the response in 20 evaluable patients will be determined, with 25 patients enrolled to ensure that 20 are evaluable

Completion of accrual will be expected in ~2 years, with an additional year of monitoring and follow up after the last patient is enrolled.

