11.3 Statistical Methods

The primary endpoints for the study are related to safety and tolerability of infusion of daratumumab in AL amyloidosis with respect to infusion reactions.

Secondary endpoints include hematologic response rate of single agent daratumumab, organ responses with respect to cardiac biomarkers and proteinuria, and time to next treatment.

The Health Related Quality of Life, as reported in SF-36, will be an exploratory endpoint.

Statistical analysis will be based on all eligible subjects. Safety analysis population includes all enrolled subjects who received at least one dose of study drug. The safety analysis population will be used for evaluating subject characteristics, treatment administration, safety endpoints, and efficacy analyses.

There will be no formal statistical hypothesis testing applied in this study. Descriptive summary statistics will be used throughout. Data will be summarized primarily by administration time and aggregated across the first 8 weeks and 2 weeks after.

Continuous variables will be summarized by the number of non-missing observations, mean, standard deviation (SD), median, minimum and maximum.

Categorical variables will be summarized by the number of non-missing observations, frequencies and percentages.

All analyses will be performed using SAS® (SAS Institute Inc., Cary, North Carolina, U.S.) version 9.4 or higher.

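### The 36-month duration estimated in Section 11.1 does not fit the 24-month course or the open-ended follow-up, and time to next treatment needs a data cutoff and a censoring rule at any duration

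*Combined protocol and SAP*

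**What the plan says.** Section 11.1, in a paragraph labelled as an estimate, states "Completion of accrual will be expected in ~2 years", "with an additional year of monitoring and follow up after the last patient is enrolled". The same section plans the trial "with 25 patients enrolled to ensure that 20 are evaluable".

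Other sections set periods for each patient:

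- Section 7.0 continues daratumumab "for up to 24 months of total study therapy", and Section 7.4.7 lists "Completion of 24 months of daratumumab" as a reason to leave protocol treatment.
- Section 9.0, footnote 5, places the end-of-treatment visit 30 days after the last dose (plus or minus 7 days). Section 12.1.2 collects serious adverse events over the same 30 days.
- Section 9.0, footnote 11, adds HBV DNA testing "Q12W for up to 6 months after last dose of study treatment". Read with Section 7.3, this concerns patients with evidence of earlier HBV infection.
- Section 7.5: "All patients will be followed until initiation of next treatment". It gives no calendar limit.

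Section 11.3 (Statistical Methods) names as secondary endpoints the hematologic response rate, "organ responses with respect to cardiac biomarkers and proteinuria, and time to next treatment". It plans descriptive statistics throughout, with continuous variables given as the mean, SD, median and range of non-missing observations. The missing-data paragraph rules out imputation by default. There is no data cutoff, censoring rule or time-to-event method.

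**The concern.** Twelve months after the last enrolment is half of the maximum treatment course. Whatever the accrual pattern, the last patient enrolled cannot finish 24 months inside the 11.1 estimate if still on treatment. Follow-up to next treatment has no end date, so no fixed duration is certain to contain it.

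If the estimate were used as the closing date, later enrolees would contribute less second-year safety data, and some would miss the 30-day window or the HBV tests. Their follow-up for time to next treatment would depend on when they entered.

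The analysis gap goes further than the calendar. At any closing date some patients may not have started another treatment. They have no recorded time, so a summary of non-missing values leaves them out and keeps the shorter times.

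**Working it through.** **Inputs.** Accrual of about 24 months, 12 months after the last enrolment, and 25 enrolled (11.1); up to 24 months of therapy (7.0, 7.4.7); 30 days after the last dose (9.0 footnote 5, 12.1.2); up to 6 months of HBV DNA testing where it applies (9.0 footnote 11). Uniform accrual is my assumption.

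**1. The plan's figure.** 24 + 12 = 36 months.

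**2. Time needed for the last enrolee's full course.** 24 + 24 = 48 months. With the 30-day visit, 48 + 1 = 49. With 6 months of HBV testing, 48 + 6 = 54.

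**3. Patients who do not fit in 36 months.** Latest entry that fits = close − time needed. Share cut short = 1 − latest entry / accrual.

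- 24-month course: 36 − 24 = month 12; 1 − 12/24 = 50%, or 12-13 of 25.
- Course plus 30 days: 36 − 25 = month 11; 1 − 11/24 = 54%, or 13-14 of 25.
- Course plus 6 months: 36 − 30 = month 6; 1 − 6/24 = 75% of those who need HBV testing.

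If accrual takes 18 months (close at 30), the first share is 1 − 6/18 = 67%. If it takes 30 months (close at 42), it is 1 − 18/30 = 40%. All of these suppose that nobody stops early.

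**4. Treatment time that could be observed.** The first half of entrants can have 24 months. The second half can have between 24 and 12, on average 18. Mean: 0.5 × 24 + 0.5 × 18 = 21.0 of 24 months.

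**5. Infusions for the last enrolee.** By week 52: 8 weekly + 8 two-weekly (weeks 9 to 23) + 7 four-weekly (weeks 25 to 49) = 23. By week 104: 8 + 8 + 20 = 36.

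**6. Time to next treatment.** The documents give no expected median, so I assume exponential times with medians m of 12, 24 and 36 months, and λ = ln 2 / m. With a close at 36 months, follow-up is uniform between 12 and 36 months. The share with an event is

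p = 1 − (e^(−12λ) − e^(−36λ)) / (24λ).

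For m = 24, λ = 0.02888 and p = 1 − (0.7071 − 0.3536)/0.6931 = 0.490; 25 × 0.490 = 12.2 events. The median among patients with events comes from the density λe^(−λt) × G(t), rescaled to total 1. Here G(t) = 1 up to month 12 and (36 − t)/24 from month 12 to 36. For a close at month 49 with everyone followed to that date, 12 and 36 become 25 and 49.

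| True median (months) | Events of 25, close at 36 | Median among events only | Events of 25, close at 49 | Median among events only |
|---|---|---|---|---|
| 12 | 18.2 | 7.9 | 21.8 | 9.9 |
| 24 | 12.2 | 9.7 | 16.2 | 13.6 |
| 36 | 9.1 | 10.5 | 12.6 | 15.1 |

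The chance that the last enrolee is still event-free at month 36 is e^(−12λ): 50%, 71% and 79%.

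The events-only median is too low at both closing dates. A later close reduces the bias but does not remove it.

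**The case against.** The strongest reply is that 11.1 is a forecast and orders nothing. Its durations are labelled as estimated, no section closes the study at month 36, and the removal criteria in 7.4 contain no study-closure item. Section 7.5 is explicit, and the other windows run from each patient's own last dose. This stands. A reader might infer that later enrolees will be cut off, but the documents support only the conditional: they would be, if the estimate governed.

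Four further points stand in whole or in part.

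- A reader might infer that the plan intends to analyse time to next treatment without censoring. It does not say so. It is silent on censoring, and the finding is an omission combined with a general rule on non-missing values.
- Administrative censoring by enrolment date is not a bias in itself. The bias comes from leaving event-free patients out, so lengthening the study is not a remedy on its own.
- Twenty-four months is a maximum. Progression, toxicity, complete response, withdrawal or myeloma can end treatment earlier, and the 54-month figure concerns only the HBV subgroup.
- A reader might infer a threat to the primary endpoint. Section 3.1 reports infusion reactions in 46% at the first infusion, 5% at the second and 4% later. Section 11.3 aggregates data over the first 8 weeks and the 2 weeks after. Even with a close at month 36, every patient could have 12 months of treatment.

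None of this reconciles the sections. If 7.5 governs, the 11.1 duration is too short. If 11.1 governs, the course and follow-up cannot be delivered for later enrolees who stay on treatment.

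**Conclusion.** The inconsistency holds on the protocol's own figures: about 36 months estimated, against 48 for the last enrolee's full course and about 49 with the 30-day visit. The ceiling of 23 of 36 infusions for the last enrolee needs no assumption about accrual, only that the study closes 12 months after that enrolment. The 12-13 of 25 is an upper bound that rests on uniform accrual over 24 months and no earlier stop. Whether any data would be lost depends on which section governs, and the documents do not settle that.

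The gap in the analysis of time to next treatment holds at any duration, because 7.5 has no end date. The direction of the bias is clear if the rule on non-missing values is applied to this endpoint. Its size in the table depends on the assumed exponential medians.

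This is worth correcting before analysis. It does not undermine the primary endpoint.

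**What to change.** 1. Reconcile 11.1 with 7.0, 7.4.7 and 7.5. Either restate the duration as about 24 months of accrual plus up to 24 months of therapy plus the 30-day visit (about 49 months, and up to about 54 only for patients needing HBV DNA monitoring after treatment), or keep 36 months and label it a data cutoff for analysis.
2. Under either choice, state a data cutoff in 11.3. Analyse time to next treatment by Kaplan-Meier, with event-free patients censored at last follow-up or at the cutoff, in place of the mean, SD and median of non-missing values.

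The text change is a few sentences, with no extra patients and no change to any dose or treatment rule. The operational cost depends on what would otherwise happen. If patients would complete therapy under 7.0 and 7.5 anyway, only the stated calendar lengthens. If 36 months would have been enforced, the longer duration adds visits and infusions for later enrolees: at most 36 − 23 = 13 infusions for the last patient, and at most 25 × (24 − 21) = 75 patient-months of treatment in all, under uniform accrual and no earlier stop.

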11.2 Interim Analysis

The study will be temporary closed for an interim analysis after the first 5 patients have completed at least 3 doses. At this time the Medical Monitor will review the safety results of the study. The recommendation is to consider stopping the study for safety concerns if during this time (3 doses for the first 5 patients) 3 or more grade 4 or 5 adverse events clearly related to study drug are recorded. If 3 or more out of the first 5 patients experience a Grade 3 infusion reaction clearly related to study drug in either of the first 3 doses, the protocol will be re-evaluated to consider modifying the schedule of daratumumab (for example, split the first dose of daratumumab over two days or adding mandatory concomitant medications). If fewer than 3 out of the first 5 patients experience a Grade 3 infusion reaction in either of the first 3 doses, the study will re-open and enrollment will be expanded to an additional cohort of subjects.

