Infusion rates for daratumumab administration:

	Dilution volume	Initial rate (1 st hour)	Rate increment ^a	Maximum rate
First infusion	1000 mL	50 mL/hour	50 mL/hour every hour	200 mL/hour
Second infusion ^b	500 mL	50 mL/hour	50 mL/hour every hour	200 mL/hour
Subsequent infusion ^c	500 mL	100 mL/hour	50 mL/hour every hour	200 mL/hour

^a Consider incremental escalation of the infusion rate only in the absence of infusion reactions.

^b Use a dilution volume of 500 mL only if there were no Grade 1 (mild) or greater infusion reactions during the first 3 hours of the first infusion. Otherwise, continue to use a dilution volume of 1000 mL and instructions for the first infusion.

^c Use a modified initial rate for subsequent infusions (i.e. third infusion onwards) only if there were no Grade 1 (mild) or greater infusion reactions during a final infusion rate of ≥ 100 mL/hr in the first two infusions. Otherwise, continue to use instructions for the second infusion.

Daratumumab will be administered at the FDA-approved dose of 16mg/kg as an intravenous infusion. Weight from screening visit will be used for initial dosing and throughout treatment period but will be recalculated for weight change $\geq 10\%$. It will be administered weekly from weeks 1 to 8, followed by every 2 weeks from weeks 9 to 24, and then every 4 weeks thereafter until progression or unacceptable toxicities, for up to 24 months of total study therapy.

The first infusion of daratumumab (in 1000 mL) will be administered at an initial rate of 50 mL/hour to be escalated hourly by 50 mL/hour to a maximum rate of 200 mL/hour.

The second infusion of daratumumab will be administered in 500 mL if no grade 1 or greater reactions have occurred throughout the first 3 hours of the first infusion. The second infusion will be administered at an initial rate of 50 mL/hour to be escalated hourly by 50 mL/hour to a maximum rate of 200 mL/hour

The third and subsequent doses will be administered in 500 mL at a starting rate of 100 mL/hour to be escalated hourly by 50 mL/hour to a maximum rate of 200 mL/hour as long as no \geq Grade 1 infusion reactions occur during a final infusion rate of ≥ 100 mL/hr in the first two infusions.

Infusion reactions of any grade will lead to the temporary interruption or slowing of the infusion, as well as management of symptoms. Depending on the grade/severity of the reaction, this may require the permanent discontinuation of the drug.

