For Grade 1-2 infusion reactions, daratumumab can be resumed at half the rate at which the reaction occurred. Further escalation of the rate is still possible providing the patient does not experience any further reactions.

For Grade 3 reactions, the infusion can be restarted at half the rate once the intensity of the reaction has decreased to a Grade 2 level or lower. Further escalation of the rate is still possible providing the patient does not experience any further reactions. The above instructions can be repeated if another Grade 3 reaction occurs. Permanent discontinuation of daratumumab should be undertaken if a third Grade 3 or greater reaction occurs.

For Grade 4 reactions (life threatening), daratumumab should be discontinued permanently.

Non-reaction Daratumumab-Related Toxicity Management

The criteria for a dose delay are:

- Grade 4 hematologic toxicities
- Grade 3 thrombocytopenia with bleeding
- Febrile neutropenia of any grade
- Neutropenia with infection, of any grade
- Grade 3 or higher non-hematologic toxicities with the following exceptions:
 - Grade 3 nausea that responds to antiemetic treatment within 7 days
 - Grade 3 vomiting that responds to antiemetic treatment within 7 days
 - Grade 3 diarrhea that responds to antidiarrheal treatment within 7 days
 - Grade 3 fatigue that was present at baseline or that lasts for <7 days after the last administration of daratumumab
 - Grade 3 asthenia that was present at baseline or that lasts for <7 days after the last administration of daratumumab

Daratumumab Delays

Administration of daratumumab may be restarted upon recovery from toxicity to Grade 2 or baseline, with the exception that Grade 2 laryngeal edema or Grade 2 bronchospasm must be fully recovered. If more than 2 consecutive planned doses of daratumumab are missed due to adverse events, treatment should be permanently discontinued. If 2 consecutive doses of daratumumab are missed for any reason other than adverse events, this should be brought to the attention of the Sponsor at the earliest possible time and study treatment should be discontinued, unless, upon consultation with the sponsor and the review of data, continuation is agreed upon.

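### Section 11.2 makes the review of the first 5 patients the gate to further enrollment but does not hold enrollment until it, so a patient (usually none or one) could be dosed ahead of it (minor)

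*Combined protocol and SAP*

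**What the plan says.** Section 11.2 sets the pause: "The study will be temporary closed for an interim analysis after the first 5 patients have completed at least 3 doses". The Medical Monitor then reviews safety under two numerical guides, both confined to the first 5 patients and their first 3 doses:

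- Stopping is considered if "3 or more grade 4 or 5 adverse events clearly related to study drug are recorded".
- The way daratumumab is scheduled is re-evaluated if 3 or more of the 5 have a Grade 3 infusion reaction clearly related to the drug. Splitting the first dose over two days is given as an example of a possible change.

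If fewer than 3 of the 5 have such a reaction, "the study will re-open and enrollment will be expanded to an additional cohort of subjects".

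Section 11.1 gives the size, "with 25 patients enrolled to ensure that 20 are evaluable", and the pace, "Completion of accrual will be expected in ~2 years". Section 3.1 gives the early schedule: "It will be administered weekly from weeks 1 to 8". Section 8.0 bears on how long 3 doses can take, and on whether they are completed at all: "If more than 2 consecutive planned doses of daratumumab are missed due to adverse events, treatment should be permanently discontinued", and "For Grade 4 reactions (life threatening), daratumumab should be discontinued permanently".

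No section caps the first cohort at 5, holds enrollment or first dosing once patient 5 has started, or staggers patients.

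**The concern.** A review that decides whether more patients are enrolled works as a gate only if nobody passes it beforehand. Here the gate closes when the last of the 5 finishes dose 3, which is at least two weeks after patient 5 starts. During that time patients 6 onward may be enrolled and given a first infusion.

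Two things are at stake. Such a patient would have a first infusion before a review that may change how the first infusion is given. That patient's events would also fall outside the counts on which the two guides rest, because both refer to the first 5 patients only.

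There is a related gap in the trigger. A patient who stops permanently at dose 1 or 2 never completes 3 doses. Read literally, the condition for closing is then not met, and the text does not say whether the patient is replaced, counted or ignored. This would happen in just the circumstances where the review matters most.

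**Working it through.** **The plan's own figure.** Section 11.1 enrolls 25 to obtain 20 evaluable: 20/25 = 0.80, and 20/0.80 = 25. This is consistent and not in dispute. The plan gives no figure for patients dosed before the review, so that is derived here.

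**Inputs.**
- Accrual: 25 patients (Section 11.1) in about 24 months (Section 11.1). The rate is 25/24 = 1.04 per month, or 25/730.5 = 0.0342 per day.
- Window without delay: weekly dosing (Sections 3.1 and 7.0) puts doses 1, 2 and 3 on days 1, 8 and 15, so 14 days.
- Window with delay: Section 8.0 requires permanent discontinuation only when more than 2 consecutive doses are missed for adverse events. Two missed weekly doses give 14 + 2 × 7 = 28 days.

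**Assumptions.** First doses arrive as a Poisson process at the constant average rate, and patient 5 is the last of the five to reach dose 3.

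**Formulas.** Expected extra patients m = rate per day × days. P(at least one) = 1 − exp(−m). P(two or more) = 1 − exp(−m)(1 + m).

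**At the planned pace.**
- 14 days: m = 0.0342 × 14 = 0.48. P(at least one) = 1 − exp(−0.479) = 38%. P(two or more) = 8%. P(none) = 62%.
- 28 days: m = 0.0342 × 28 = 0.96. P(at least one) = 1 − exp(−0.958) = 62%. P(two or more) = 25%.

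**Sensitivity to the accrual period.** The plan says only about 2 years; 18 and 30 months are assumed bounds.

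| Accrual | Window | Expected extra | P(at least one) | P(two or more) |
|---|---|---|---|---|
| 18 months | 14 days | 0.64 | 47% | 14% |
| 18 months | 28 days | 1.28 | 72% | 37% |
| 24 months | 14 days | 0.48 | 38% | 8% |
| 24 months | 28 days | 0.96 | 62% | 25% |
| 30 months | 14 days | 0.38 | 32% | 6% |
| 30 months | 28 days | 0.77 | 54% | 18% |

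The 28-day window is not a strict ceiling. The Section 8.0 limit applies to consecutive missed doses, and a delay in any of the five can postpone closure.

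**With a hold from patient 5's first dose.** The number of extra patients dosed before the review is 0 by construction.

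**The trigger when a patient stops early.** Section 11.2 needs all 5 to complete at least 3 doses. Section 8.0 ends treatment permanently after a Grade 4 infusion reaction. If that occurs at dose 1 or 2, only 4 of the first 5 can ever satisfy Section 11.2, and no sentence says what follows.

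**The case against.** **Intent.** The natural reading of re-opening the study and adding a cohort is that the first cohort is 5, so this is a gap in wording more than a flaw in design. That stands as a reading of intent. It does not supply the missing rule: the only sentence that stops enrollment acts at dose 3.

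**Size.** With no dose delay, the likeliest outcome (62%) is that nobody is dosed early. The 28-day figures need a patient to miss two consecutive doses. This stands and limits the severity.

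**Chance that the review changes anything.** A reader might set the 46% first-infusion reaction rate in Section 3.1 against the early patients. That figure is for any grade in myeloma, whereas the review acts on Grade 3 infusion reactions or on grade 4 or 5 events; the same section calls severe reactions rare (under 2% each). It gives no overall Grade 3 rate. For assumed per-patient rates p of 5%, 10% and 20%, the chance of 3 or more in 5, 10p³(1−p)² + 5p⁴(1−p) + p⁵, is 0.12%, 0.86% and 5.8%. Multiplied by 38%, the chance that a patient is dosed early and the infusion-reaction guide is then met is roughly 0.04% to 2%. This treats the two as independent and leaves out the grade 4 or 5 guide. Patients with AL amyloidosis may also differ from those with myeloma. The point stands as a reason to call the issue minor.

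**Other safeguards.** Section 12.0 provides continuing evaluation of toxicity and 48-hour reporting of deaths and unanticipated problems to the Medical Monitor. Sections 7 and 8.0 give premedication and reaction management for every patient. So it would be wrong to infer that a sixth patient is unmonitored. But Section 12.0 says it has no preset criteria for early termination, and it contains no enrollment hold.

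**Analysis.** A reader might infer that patients dosed early would belong to no cohort and be lost to the analysis. Section 11.3 rules that out: everyone enrolled who receives a dose is in one safety population, summarized descriptively.

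**Conclusion.** The gap is real and minor. As written, Section 11.2 lets patients be dosed before the review that is meant to decide whether more are enrolled, and its trigger does not cover permanent discontinuation before dose 3. At the plan's average pace the expected number dosed early is about 0.5 (38% chance of at least one), rising to about 1 (62%) if two doses are missed. In practice this is usually none or one.

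These figures rest on constant Poisson accrual over about 24 months and on enrollment translating directly into first doses. Larger exposures follow from a faster pace: at 2 patients per month, 0.92 expected and 60% over 14 days, or 1.84 and 84% over 28 days. No such pace appears in the documents, so those figures should not be attributed to the plan.

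Nor do the documents show that anyone was dosed early. They do not say whether the review has taken place, although version 12 is dated 2/26/19 and Section 7.3 already refers to patients on treatment.

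**What to change.** Amend Section 11.2 to say:

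1. After patient 5 has received a first dose, no further patient receives a first dose until the Medical Monitor's review is recorded. This governs entry of new patients only, not treatment of those already on study.
2. The review takes place once each of the first 5 has either completed 3 doses or permanently discontinued. Those who discontinued stay in the denominator and their events count toward both guides. Without this part, the hold in item 1 could never be lifted if a patient stopped before dose 3.

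If the review has already taken place, report instead how many patients had received a first dose before it.

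The cost is two sentences and an accrual hold that starts about 2 to 4 weeks earlier (14 to 28 days) in an accrual of about 24 months. The length of the review is not stated, so patients already screened may wait. Some may need repeat tests, because the Section 9.0 footnotes require most screening tests within 28 days of starting study drug.
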